**Table 2. Derivation Rules for Confirmed Best Overall Response per IMWG Response Criteria**

Scenario	Timepoint Response at:			BOR
	Assessment 1	Assessment 2	Assessment 3	
1	sCR	sCR		sCR
2	sCR	NE	sCR	
3	CR/VGPR/PR/MR/SD/PD c	sCR	sCR	
4	CR	sCR/CR		CR
5	sCR/CR	CR		
6	CR	NE	CR	
7	VGPR/PR/MR/SD/PD c	CR	CR	
8	VGPR	sCR/CR/VGPR		VGPR
9	sCR/CR/VGPR	VGPR		
10	VGPR	NE	VGPR	
11	PR/MR/SD/PD c	VGPR	VGPR	
12	PR	sCR/CR/VGPR/PR		PR
13	sCR/CR/VGPR/PR	PR		
14	PR	NE	PR	
15	MR/SD/PD c	PR	PR	
16	MR	sCR/CR/VGPR/PR/MR		MR
17	sCR/CR/VGPR/PR/MR	MR		
18	MR	NE	MR	
19	SD/PD c	MR	MR	
20	SD	No further assessments		SD a
21	SD	sCR/CR/VGPR/PR/MR /SD/PD	No further assessments	
22	sCR/CR/VGPR/PR/MR	NE/PD or no further assessment	No further assessments	
23	PD c	PD (any reason) including PD after initiation of new anticancer therapy		PD
24	PD c	Participant died due to disease before further disease assessment (including death due to disease under study after initiation of new anticancer therapy)		

090177e1993a4a6d\Approved\Approved On: 31-Jan-2022 16:54 (GMT)

Scenario	Timepoint Response at:			BOR
	Assessment 1	Assessment 2	Assessment 3	
25	PD (due to EMD, or bone marrow plasma cells) b	sCR/CR/VGPR/PR/MR /SD/NE/PD or no further assessments	No further assessments	
26	Death (due to disease under study)			
27	Death (not due to disease under study) before initiation of new anticancer therapy			
28	NE	No further assessment		
29	NE	NE/PD c	No further assessments	NE
30	PD c	sCR/CR/VGPR/PR/MR /SD/NE	No further assessments	
EMD = extramedullary disease; IMWG = International Myeloma Working Group, sCR = stringent complete response, CR = complete response, PR = partial response, VGPR = very good partial response, SD = stable disease, PD = progressive disease, NE = not evaluable. a. SD does not need to be confirmed. b. PD due to EMD (includes any new lesion, increased extramedullary or paramedullary lesions, plasmacytomas), or bone marrow plasma cells does not need to be confirmed. c. PD due to reasons other than EMD, or bone marrow plasma cells.				

### 6.2.2. Complete Response Rate

CRR is defined as the proportion of participants with a confirmed CR/sCR per IMWG criteria as determined by investigator.

Point estimates of CRR will be calculated along with corresponding 2-sided exact 95% CIs using the Clopper-Pearson method.

### 6.2.3. Progression-free Survival

PFS is defined as the time from the date of first dose until the initial documentation of PD date that is subsequently confirmed per IMWG criteria as determined by investigator or death due to any cause, whichever occurs first. The rules for PD confirmation are described in [Table 2](#).

PFS will be calculated as follows:

$$\text{PFS (months)} = [\text{date of event or censoring} - \text{date of first dose} + 1] / 30.4375.$$

PFS will be censored as follows:

- For participants who do not have an event (confirmed PD per IMWG criteria or death due to any cause), censoring will occur on the date of the last adequate disease assessment;

- For participants who start a new anticancer therapy (as defined in [Section 5.2.6 in the master SAP](#)) prior to an event, censoring will occur on the date of the last adequate disease assessment before the new anticancer therapy;
- For participants with an event after a gap of 2 or more missing disease assessments, censoring will occur on the date of the last adequate disease assessment before the gap;
- Participants who do not have an adequate post-baseline disease assessment will be censored on the date of first dose of study intervention unless death occurs on or before the time of the second planned disease assessment (ie,  $\leq 70$  days after the date of first dose) in which case the death will be considered an event.

The censoring and event date options to be considered for the PFS analysis are presented in Table 3. Adequate post-baseline disease assessment is defined in [Section 5.2.10 in the master SAP](#).

**Table 3. Outcome and Event Dates for PFS Analyses**

Scenario	Date of Event/Censoring	Outcome
Progression or death 1. After at most 1 missing or inadequate post-baseline disease assessment or 2. $\leq 70$ days after date of first dose of study intervention	Date of progression or death	Event
Progression or death after 2 or more missing or inadequate disease assessments a	Date of last adequate assessment a documenting no PD prior to new anticancer therapy or missed disease assessments	Censored
No progression or death		
New anticancer therapy given prior to PD or death		

a. If there are no adequate post-baseline disease assessments prior to PD or death, then the time without adequate assessment should be measured from the date of first dose of study intervention; if the criteria were met, the censoring will be on the date of first dose of study intervention.

PFS = progression-free survival; PD = progressive disease

Kaplan-Meier estimates (product-limit estimates) will be presented and displayed graphically where appropriate, together with a summary of associated statistics including the median PFS time with 2-sided 95% CIs. The CIs for the median will be calculated according to Brookmeyer and Crowley, 1982.

The PFS rate at 3, 6, 9, 12, 18, and 24 months (and in subsequent 12-month increments while there are participants still at risk) will be estimated with corresponding two-sided 95% CIs. The CIs for the survival function estimates at the timepoints defined above will be derived using the log(-log) method according to Kalbfleisch and Prentice (conftype=loglog default option in SAS Proc LIFETEST). The estimate of the standard error will be computed using

Greenwood’s formula. Frequency (number and percentage) of participants with each event type (PD or death) and censoring reasons will be presented along with the overall event and censor rates.

Reasons for censoring will be summarized according to the categories in Table 4. If a participant meets multiple definitions for censoring the list will be used to define the hierarchy.

**Table 4. PFS Censoring Reasons and Hierarchy**

Hierarchy	Condition	Censoring Reason
1	Start of new anticancer therapy before event.	Start of new anticancer therapy
2	Event after 2 or more missing or inadequate post-baseline disease assessment after date of first dose	Event after missing or inadequate assessments a
3	No event and [withdrawal of consent date ≥ date of first dose or End of study (EOS) = Participant refused further follow-up]	Withdrawal of consent
4	No event and lost to follow-up in any disposition page	Lost to follow-up
5	No event and [EOS present or disposition page for any EPOCH after screening says participant will not continue into any subsequent phase of the study] and no adequate post-baseline disease assessment	No adequate postbaseline disease assessment
6	No event and none of the conditions in the prior hierarchy are met	Ongoing without an event

a. More than 70 days after last adequate disease assessment.

The PFS time or censoring time and the reasons for censoring will also be presented in a data listing.

#### 6.2.4. Duration of Response

DOR is defined, for participants with an objective response per IMWG criteria as determined by investigator, as the time from the first documentation of objective response that is subsequently confirmed, until the initial documentation of PD date that is subsequently confirmed per IMWG criteria, or death due to any cause, whichever occurs first. The rules for PD confirmation are described in [Table 2](#).

DOR will be calculated as follows:

$$\text{DOR (months)} = (\text{date of event or censoring} - \text{first date of objective response} + 1) / 30.4375$$

The censoring rules for DOR are as described for PFS in [Section 6.2.2 in the master SAP](#) except that participants will not be censored for no adequate post-baseline assessment, as only participants with an objective response are included in the analysis of DOR.

If at least 3 participants achieve an objective response and subsequently have an event, DOR will be estimated using the same Kaplan-Meier method as described for PFS in [Section 6.2.3](#) and displayed graphically where appropriate. Otherwise only listings will be provided.

The DOR rate at 3, 6, 9, and 12 months (and in subsequent 6-month increments while there are participants still at risk) will be estimated with corresponding two-sided 95% CIs.

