### 6.2.2. Progression-free Survival

PFS is defined as the time from the date of first dose until PD per IMWG criteria as determined by investigator or death due to any cause, whichever occurs first. PFS will be calculated as follows:

$$\text{PFS (months)} = [\text{date of event or censoring} - \text{date of first dose} + 1] / 30.4375.$$

PFS will be censored as follows:

- For participants who do not have an event (PD per IMWG criteria or death due to any cause), censoring will occur on the date of the last adequate disease assessment;
- For participants who start a new anticancer therapy (as defined in [Section 5.2.6](#)) prior to an event, censoring will occur on the date of the last adequate disease assessment before the new anticancer therapy;
- For participants with an event after a gap of 2 or more missing disease assessments, censoring will occur on the date of the last adequate disease assessment before the gap;
- Participants who do not have an adequate baseline disease assessment or who do not have an adequate post-baseline disease assessment will be censored on the date of first dose of study intervention unless death occurs on or before the time of the second planned disease assessment (ie,  $\leq 8$  weeks after the date of first dose) in which case the death will be considered an event.

The censoring and event date options to be considered for the PFS analysis are presented in [Table 4](#). Adequate baseline disease assessment and adequate post-baseline disease assessment are defined in [Section 5.2.9](#) and [Section 5.2.10](#), respectively.

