**Table 5. PFS Censoring Reasons and Hierarchy**

Hierarchy	Condition	Censoring Reason
1	No adequate baseline assessment	No adequate baseline assessment
2	Start of new anticancer therapy before event.	Start of new anticancer therapy
3	Event after 2 or more missing or inadequate post-baseline disease assessment after date of first dose	Event after missing or inadequate assessments a
4	No event and [withdrawal of consent date $\geq$ date of first dose or End of study (EOS) = Participant refused further follow-up]	Withdrawal of consent
5	No event and lost to follow-up in any disposition page	Lost to follow-up
6	No event and [EOS present or disposition page for any EPOCH after screening says participant will not continue into any subsequent phase of the study] and no adequate post-baseline disease assessment	No adequate postbaseline disease assessment
7	No event and none of the conditions in the prior hierarchy are met	Ongoing without an event

a. More than 62 days after last adequate disease assessment while on treatment with study intervention; more than 70 days after discontinuing study intervention without PD.

The PFS time or censoring time and the reasons for censoring will also be presented in a data listing.

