### 6.2.3. Duration of Response

DOR is defined, for participants with an OR per IMWG criteria as determined by investigator, as the time from the first documentation of OR that is subsequently confirmed, until PD per IMWG criteria, or death due to any cause, whichever occurs first. DOR will be calculated as follows:

$$\text{DOR (months)} = [\text{date of event or censoring} - \text{first date of OR} + 1] / 30.4375$$

The censoring rules for DOR are as described for PFS in [Section 6.2.2](#), except that participants will not be censored for inadequate baseline assessment or for no adequate post-baseline assessment, as only participants with an OR are included in the analysis of DOR.

If at least 3 participants achieve an OR and subsequently have an event, DOR will be estimated using the same Kaplan-Meier method as described for PFS in [Section 6.2.2](#) and displayed graphically where appropriate. Otherwise only listings will be provided.

The DOR rate at 3, 6, 9, and 12 months (and in subsequent 6-month increments while there are participants still at risk) will be estimated with corresponding two-sided 95% CIs.

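### Sub-study B takes its duration-of-response censoring from the master SAP's PFS section, which would censor a responder without an adequate baseline before the response and uses a different on-treatment gap window from Sub-study B's own PFS

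*SAP*

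**What the plan says.** - **Sub-study B SAP, 6.2.4 (DOR).** Censoring follows PFS in "Section 6.2.2 in the master SAP", with one exception: "except that participants will not be censored for no adequate post-baseline assessment". For the Kaplan-Meier method, the same section cites Sub-study B's own PFS section, 6.2.3. Section 6.2.5 applies the DOR censoring rules to DOCR.
- **Master SAP, 6.2.2 (PFS).** Early deaths aside, the day treatment began is the censoring date for two groups: "Participants who do not have an adequate baseline disease assessment or who do not have an adequate post-baseline disease assessment will be censored". Table 5 ranks an inadequate baseline first among the censoring reasons. Its footnote sets the gap at "More than 62 days after last adequate disease assessment while on treatment with study intervention", and at 70 days after discontinuation.
- **Master SAP, 6.2.3 (DOR).** This section waives both rules: "participants will not be censored for inadequate baseline assessment or for no adequate post-baseline assessment".
- **Sub-study B SAP, 6.2.3 (PFS).** There is no adequate-baseline rule. The Table 4 footnote gives a single gap: "More than 70 days after last adequate disease assessment".
- **Sub-study A SAP, 6.2.3 (DOR).** It carries the same single exception as Sub-study B but refers to its own PFS section, which has no adequate-baseline rule.

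**The concern.** The single exception in Sub-study B 6.2.4 is enough only if the PFS section it refers to has no baseline rule. The master section does have one, and nothing in 6.2.4 turns it off. Two things follow from the text as written.

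1. A responder whose baseline does not meet the definition in master SAP 5.2.9 is censored at first dose. DOR starts at first response, which is later, so the time at risk is zero or negative and any later progression is lost as an event.
2. PFS and DOR apply different gap windows on treatment. One progression in one participant can then count as an event in one analysis and be censored in the other, with no reason given.

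At stake is the internal consistency of two secondary endpoints in a small cohort. A programmer would also have to decide, after seeing the data, how to handle impossible durations.

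**Working it through.** **Inputs**

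| Input | Value | Source |
|---|---|---|
| DOR in months | (E - R + 1) / 30.4375, where E is the event or censoring day and R the first-response day | Sub-study B 6.2.4 |
| E when baseline is inadequate | day 1 (first dose) | Master 6.2.2, Table 4 |
| On-treatment gap limit for DOR | 62 days | Master Table 5, footnote a |
| Off-treatment gap limit for DOR | 70 days | Master Table 5, footnote a |
| Gap limit for PFS | 70 days | Sub-study B Table 4, footnote a |
| Participants at the RP2D | up to 20, including 6 from escalation | Sub-study B 2.2 and 5.1.1.2 |

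**The plan's own figure.** Master Table 4 explains 62 days as two cycles with a 3-day visit window: 2 x (28 + 3) = 62. This reproduces. No basis is given for 70 days. It is consistent with 2 x (28 + 7), using the one-week window for follow-up assessments in protocol 7.1.2.

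**Responder without an adequate baseline.** Setting E = 1 gives DOR = (1 - R + 1) / 30.4375 = (2 - R) / 30.4375. The response days below are assumptions, because the Sub-study B schedule of activities is not supplied.

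| First response (R) | DOR as written |
|---|---|
| day 2 | 0.00 months |
| day 29 | -27 / 30.4375 = -0.89 |
| day 43 | -41 / 30.4375 = -1.35 |
| day 71 | -69 / 30.4375 = -2.27 |

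The value is negative for any response from day 3 on. If the baseline rule did not apply and the last adequate assessment fell on day 400 (also assumed), the day-43 responder would have (400 - 43 + 1) / 30.4375 = 11.76 months.

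**Gap from last adequate assessment to progression or death**

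| Gap | PFS | DOR, on treatment | DOR, off treatment |
|---|---|---|---|
| 62 days or less | event | event | event |
| 63 to 70 days | event | **censored** | event |
| 71 days or more | censored | censored | censored |

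**Could such a responder exist?** Master 5.2.9 requires every baseline disease assessment to fall within 28 days of first dose. Master 3.4 expects some baseline values outside the protocol window and treats them as deviations without excluding them. Master 5.2.9 also asks for serum M-protein above 0.5 g/dL where protocol Appendix 11 accepts 0.5 g/dL or more. That difference matters only for a participant at exactly 0.5 g/dL who also fails the urine and free-light-chain criteria. Sub-study B's response definitions do not require an adequate baseline.

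**How likely is at least one?** No rate is given. If each of r responders lacked an adequate baseline with probability q, the chance of at least one is 1 - (1 - q)^r:

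| r (assumed) | q = 2% | q = 5% | q = 10% |
|---|---|---|---|
| 10 | 0.18 | 0.40 | 0.65 |
| 20 | 0.33 | 0.64 | 0.88 |

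**Effect on the curve.** A censored time at or below zero never contributes to a risk set. If the lost responder would have stayed event-free, the first Kaplan-Meier step changes from 1/20 to 1/19 (0.3 percentage points) with 20 responders, or from 1/10 to 1/9 (1.1 points) with 10. The effect is larger if the lost responder had an event.

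**The case against.** **The master SAP cited may not be the one supplied.** Sub-study B cites master Sections 6.5.1, 6.5.2, 6.5.4, 6.5.5 and 6.6 for material that stands in 6.6.x and 6.7 of the March 2021 document. It also refers to master Section 4 for DLT evaluability, where the supplied text has a 35-day window and no exposure minimum for lenalidomide or dexamethasone; Sub-study B uses 42 days. A later master version, with a different 6.2.2, cannot be excluded. This stands as a real uncertainty. It does not remove the point, because the pointers to 5.2.6, 5.2.10 and 6.2.2 all match the supplied text.

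**The number affected may be zero.** A reader might infer that some responders will in fact receive negative durations. The documents do not support that. Eligibility waivers are barred, measurable disease is required at entry, and pre-consent imaging used as baseline must fall within 28 days. The defect is conditional on an inadequate baseline, and no count is given.

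**The curve need not move visibly.** A reader might also expect one negative value to distort the Kaplan-Meier curve. It would drop that responder instead, and the shift in the first step is small unless an event is lost. Kaplan-Meier estimation is run only if at least 3 responders have an event.

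**The gap mismatch is narrow.** It does not cover every event at 63 to 70 days: after discontinuation both documents use 70 days. The general rule, two or more missed assessments, is the same in both PFS sections; the day counts differ in the table footnotes and the early-event limits.

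**It looks like an editorial slip.** The single exception fits Sub-study B's own 6.2.3, and Sub-study A's parallel text is correct. That supports the remedy, but the text as written still specifies a wrong rule.

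**Conclusion.** The point holds in conditional form. Followed literally against the March 2021 master SAP, Sub-study B 6.2.4 censors a responder without an adequate baseline before the response starts, unless an early death counts as an event. It also separates DOR from PFS for on-treatment events 63 to 70 days after the last adequate assessment. DOCR inherits both.

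The sign of the duration follows from the formula for any response from day 3. The particular values rest on assumed response days, and the frequency is unknown. The conclusion also assumes that the supplied document is the master SAP being cited. The likeliest explanation is a wrong cross-reference, since master DOR waives the baseline rule and Sub-study A refers to its own PFS section.

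The consequence is limited. DOR and DOCR are secondary endpoints in a Phase 1b sub-study with no hypothesis and no efficacy decision rule. The correction is still worth making before analysis, because the written rule can produce impossible values.

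**What to change.** In Sub-study B SAP 6.2.4, replace the reference to "Section 6.2.2 in the master SAP" with a reference to Section 6.2.3 of the Sub-study B SAP, and keep the exception for no adequate post-baseline assessment. This removes the adequate-baseline rule and puts PFS, DOR and DOCR on the same 70-day gap. Adding a baseline exemption while leaving the pointer unchanged would cure the negative durations but not the window mismatch.

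State in the Sub-study B SAP which master SAP version and date it cites, and check the other section references against it.

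The cost is one cross-reference and one version statement. No data collection, sample size or primary analysis changes.

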### 6.2.5. Duration of Complete Response

DOCR is defined, for participants with a confirmed CR/sCR per IMWG criteria as determined by investigator, as the time from the first documentation of CR/sCR that is subsequently confirmed, until the initial documentation of PD date that is subsequently confirmed per IMWG criteria, or death due to any cause, whichever occurs first. The rules for PD confirmation are described in [Table 2](#).

DOCR will be calculated as follows:

$$\text{DOCR (months)} = [\text{date of event or censoring} - \text{first date of confirmed CR/sCR} + 1] / 30.4375$$

The censoring rules for DOCR are as described for DOR in [Section 6.2.4](#).

If at least 3 participants achieve a BOR of confirmed CR/sCR and subsequently have an event, DOCR will be estimated using the same Kaplan-Meier method as described for DOR in [Section 6.2.4](#) and displayed graphically where appropriate. Otherwise only listings will be provided.

The DOCR rate at 3, 6, 9, and 12 months (and in subsequent 6-month increments while there are participants still at risk) will be estimated with corresponding two-sided 95% CIs.

### 6.2.6. Overall Survival

OS is defined as the time from the date of first dose until death due to any cause and will be calculated in months as follows:

$$\text{OS (months)} = [\text{date of death or censoring} - \text{date of first dose} + 1] / 30.4375$$

Survival status is expected to be collected irrespective of study intervention discontinuation or participant's request to discontinue study procedures. All participants who have not withdrawn consent for further participation in the study should be followed for survival until the end of the study. OS for participants not known to have died are censored on the date of last known alive.

OS time will be estimated using the same Kaplan-Meier method and displayed graphically as described for PFS in [Section 6.2.3](#). Median OS and 2-sided 95% CI will be provided. The OS rate at 12, 24, and 36 months (and in subsequent 12-month increments while there are participants still at risk) will be estimated with corresponding two-sided 95% CIs.

Frequency (number and percentage) of participants with death events and censoring reasons will be presented along with the overall event and censor rates. The event and censoring reasons are as follows:

- Death;
- Ongoing and no death;
- Withdrawal of consent;
- Lost to follow-up.

In addition, OS will be summarized with simple descriptive statistics (mean, standard deviation, minimum, median, and maximum) for duration of follow-up, as well as reverse Kaplan-Meier method.

The OS time or censoring time and the reasons for censoring will also be presented in a listing.

